### 11.3 Screen Failures

Patients who sign an informed consent form, are not assigned to a treatment, and do not receive study drug are defined as screen failures. For all screen failures, the investigator is to maintain a screening log that documents the screening number, patient initials, and reason(s) for screen failure. This information will be tracked in the EDC system and retained in the investigator's study files.

## 12.0 CONCOMITANT TREATMENT

Concomitant treatment is permitted if the medication is not expected to interfere with the evaluation of safety or efficacy of the study drug. During the study, if the use of any concomitant treatment becomes necessary (e.g., for treatment of an adverse event), the treatment must be recorded on the eCRF, including the reason for treatment, generic name of the drug, dosage, route, and date of administration.

Patients enrolling in studies with PLX3397 who are also receiving concomitant warfarin should have their anti-coagulation status carefully monitored, especially shortly after initiation of PLX3397, for the potential need to make adjustments in warfarin dosing. In particular, INR should be obtained just prior to initiation of PLX3397, within 1-2 weeks after initiation, and periodically thereafter. Dose adjustments of warfarin should be made as medically indicated.

Although PLX3397 does not appear to inhibit CYP drug-metabolizing enzymes to an important extent, caution is warranted when administering PLX3397 to subjects taking drugs that are highly dependent on CYP3A4 for metabolism and have a narrow therapeutic index. It is not known whether systemic exposure to these medications will demonstrate an increase while patients are receiving PLX3397.

Of the five major CYP isoforms, 3A4 (BFC) may be involved in Phase I metabolism of PLX3397, with possibly CYP1A2 playing a minor role. Until information regarding exposure-toxicity and exposure-response relationships are available with PLX3397, concomitant CYP3A4 inhibitors and inducers should be administered with caution, in the event they alter the systemic exposure to PLX3397 (see [Attachment 2](#) for a list of strong CYP3A4 inhibitors and inducers). In general, strong inhibitors or inducers of CYP3A4 should be avoided unless absolutely necessary. These include anticonvulsants (phenytoin, carbamazepine, phenobarbital), mycin antimicrobials, and antiretrovirals. Strong CYP 3A4 inducers or inhibitors should be discontinued at least 14 days prior to the initiation of dosing with PLX3397.

## 13.0 PROCEDURES

### 13.1 Screening Evaluation

Within 21 days before study drug administration on C1D1 to radiation therapy, all patients will have a Screening evaluation that includes the following:

[Note: Safety assessments obtained as Standard of Care may be used for screening purposes.]

1. Sign and date an IRB/IEC-approved informed consent form before any study-specific screening procedures are performed.
2. Medical history.
3. Height, weight, vital signs (sitting blood pressure, pulse rate, respiratory rate, and temperature), and physical examination.
4. Standard 12-lead ECG.
5. Clinical laboratory evaluation [hematology, chemistry, serum pregnancy test (women of child-bearing potential); see [Attachment 1](#)]. Safety assessments obtained as Standard of Care may be used for screening purposes.
6. Availability of archival paraffin tumor block sufficient to generate at least 20 unstained slides (or at least 20 unstained slides).
7. Karnofsky performance status assessment.
8. MRI brain scan within 28 days (14 days preferred) of C1D1.
9. Recording of concomitant medications.

If screening tests and procedures are performed within 2 days prior to C1D1 PLX3397 administration and their results are available for the investigator to review within the 2-day period prior to C1D1 PLX3397 administration, the screening tests and procedures that would be repeated at C1D1 do not need to be repeated before C1D1 PLX3397 administration.

Patients who do not meet all inclusion and exclusion criteria will be noted as screen failures in the EDC system.

### 13.2 Cycle 1 Day 1 (- 2 Days), [4 week cycle]

The C1D1 visit must occur any Monday through Friday  $\geq 3$  weeks and  $\leq 5$  weeks since surgery. At this visit, all patients will return to the clinic and undergo the following procedures:

1. Weight, vital signs, neurological exam plus symptom-directed physical examination.

2. Clinical laboratory evaluation (hematology and serum chemistry).
3. For Phase 1b dose escalation patients only: Pre-dose blood sample collection for PK.
4. Pre-dose blood sample collection for PD response biomarkers and CD14/16 mononuclear cell counts.
5. Karnofsky performance status assessment.
6. MDA Symptom Inventory.
7. Recording of concomitant medications.
8. Initiation of dosing with study drug either 7 days/week or 5 days/week (Monday through Friday).
9. AE Monitoring, beginning after first dose of study drug.

### **13.3 Cycle 1 Day 8 ( $\pm$ 2 Days), [4 week cycle]**

On C1D8, all patients will return to the clinic and undergo the following procedures:

1. Vital signs, neurological exam plus symptom-directed physical examination.
2. Clinical laboratory evaluation (hematology and serum chemistry).
3. For Phase 1b dose escalation patients only: Pre-dose and 1, 2, 4, and 6 hours post-dose blood sample collection for PK.
4. Pre-dose blood sample collection for PD response biomarkers and CD14/16 mononuclear cell counts.
5. Study drug compliance.
6. Recording of concomitant medications.
7. AE monitoring.
8. Initiation of radiation therapy and temozolomide.

### **13.4 Cycle 1 Day 15 ( $\pm$ 2 Days), [4 week cycle]**

On C1D15, all patients will return to the clinic and undergo the following procedures:

1. For Phase 1b dose escalation patients only: Vital signs, neurological exam plus symptom-directed physical examination.

2. Clinical laboratory evaluation (hematology and serum chemistry).
3. For Phase 1b dose escalation patients only: Pre-dose and 1, 2, 4, and 6 hours post-dose blood sample collection for PK.
4. Study drug compliance.
5. Recording of concomitant medications.
6. AE monitoring.
7. Instruct patient to obtain C1D22 ( $\pm 2$  days) hematology evaluation (CBC, differential count, platelet count) either at study site or local laboratory.

### **13.5 Cycle 2 Day 1 ( $\pm 2$ Days), [3 week cycle]**

On C2D1, all patients will return to the clinic and undergo the following procedures:

1. Weight, vital signs, neurological exam plus symptom-directed physical examination.
2. Standard 12-lead ECG.
3. Clinical laboratory evaluation (hematology and serum chemistry).
4. Pre-dose blood sample collection for PD response biomarkers.
5. Karnofsky performance status assessment.
6. Study drug compliance.
7. Recording of concomitant medications.
8. AE monitoring.
9. Instruct patient to obtain C2D8 ( $\pm 2$  days) and C2D15 ( $\pm 2$  days) hematology evaluation (CBC, differential count, platelet count) either at study site or local laboratory.

### **13.6 Cycle 2 Day 22 ( $\pm 2$ Days), [3 week cycle]**

On C2D22, all patients will return to the clinic and undergo the following procedures:

1. Weight, vital signs, neurological exam plus symptom-directed physical examination.
2. Clinical laboratory evaluation (hematology and serum chemistry).
3. Karnofsky performance status assessment.
4. MDA Symptom Inventory.
5. Study drug compliance.

6. Recording of concomitant medications.
7. AE monitoring.
8. Instruct patient to obtain RPD8 ( $\pm 2$  days) hematology evaluation (CBC, differential count, platelet count) either at study site or local laboratory.

### **13.7 Day 1 of Cycle 3 ( $\pm 7$ Days), [4 week cycle]**

Following a 4 week recovery period, all patients will return to the clinic on C3D1 and undergo the following procedures:

1. Weight, vital signs, neurological exam plus symptom-directed physical examination.
2. Clinical laboratory evaluation (hematology and serum chemistry).
3. Pre-dose blood sample collection for PD response biomarkers.
4. Karnofsky performance status assessment.
5. MDA Symptom Inventory.
6. MRI brain scan to be obtained at the end of each even-numbered cycle.
7. Re-initiation of study drug dosing 7 days/week.
8. Initiation of temezolomide adjuvant therapy. Temozolomide is taken orally once daily for 5 days followed by 23 days without treatment for each cycle beginning with C3D1.
9. Recording of concomitant medications.
10. AE monitoring.

### **13.8 Day 22 of Cycle 3 ( $\pm 2$ Days), [4 week cycle]**

On C3D22, all patients will return to the clinic and undergo the following procedures:

1. Weight, vital signs, neurological exam plus symptom-directed physical examination.
2. Clinical laboratory evaluation (hematology and serum chemistry).
3. Karnofsky performance status assessment.
4. MDA Symptom Inventory.
5. Study drug compliance.

6. Recording of concomitant medications.
7. AE monitoring.

### **13.9 Day 22 of Cycle 4+ ( $\pm$ 7 Days), [4 week cycle]**

On Day 22 of Cycle 4 and all subsequent cycles, all patients will return to the clinic and undergo the following procedures:

1. Weight, vital signs, neurological exam plus symptom-directed physical examination.
2. Clinical laboratory evaluation (hematology and serum chemistry).
3. Karnofsky performance status assessment.
4. MDA Symptom Inventory.
5. MRI brain scan to be obtained at the end of each even-numbered cycle.
6. Study drug compliance.
7. Recording of concomitant medications.
8. AE monitoring.

### **13.10 Assessments After 01 October 2017 to Be Performed Approximately Every 12 Weeks**

**Commencing on 01 October 2017, patient visits, clinical laboratory testing, and MRI brain scans will be performed approximately every 12 weeks (please refer to the [TRIAL FLOW CHART – Phase 2](#) for details).**

### **13.11 End of Treatment**

All patients who permanently discontinue PLX3397 are expected to return to the clinic within 30 days and undergo the following procedures:

1. Weight, vital signs, neurological exam plus symptom-directed physical examination.
2. Standard 12-lead ECG.
3. Clinical laboratory evaluation [hematology, serum chemistry, serum pregnancy test (women of child-bearing potential)].
4. Karnofsky performance status assessment.
5. MDA Symptom Inventory.

6. Study drug compliance.
7. Recording of concomitant medications.
8. AE monitoring.

### 13.12 Continued Dosing

Patients may continue once-daily adjuvant temozolomide (Day 1-5 of a 28-day cycle) for up to 12 cycles as long as there is no disease progression or unacceptable toxicity and PLX3397 twice daily (28 days of a 28-day cycle) for as long as there is no disease progression or unacceptable toxicity. After discontinuation of study drug, patients will continue to be followed for OS every 6 months. Study visits will occur at approximately 4-week intervals. Brain MRI scans should be obtained approximately every 8 weeks. The same method used at Screening should be used for all serial measurements.

### 13.13 Dose Levels for the Phase 1b Portion

#### 13.13.1 Dose Escalation

A total of approximately 7 patients will be enrolled in each dose level (see [Table 2](#)). The starting dose level of PLX3397 will be 800 mg/day administered 7 days/week (Cohort 1).

**Table 2: PLX3397 Dosing Cohorts**

Cohort	Combination PLX3397/RT/TMZ		Adjuvant PLX3397/TMZ	
	PLX3397 Dose	PLX3397 Schedule	PLX3397 Dose	PLX3397 Schedule
-2	600 mg/day	5 days/week (M-F) b	800 mg/day b	7 days/week
-1	600 mg/day	7 days/week a	600 mg/day a 800 mg/day b	7 days/week
1	800 mg/day	7 days/week a 5 days/week (M-F) b	1000 mg/day b	7 days/week
2	1000 mg/day	5 days/week (M-F) b	1200 mg/day b	7 days/week

a Amendment 1.

b Amendment 2.

Study drug will be administered orally using a capsule formulation (200 mg per capsule). The total daily dose of PLX3397 will be divided and administered BID. For an uneven number of capsules, the larger dose will be administered in the morning.

For combination PLX3397/RT/TMZ PLX3397 treatment, dose escalation to the next highest cohort may occur after all patients have completed the 11-week DLT-observation period (i.e., 1-week PLX3397 monotherapy; 6-week PLX3397/RT/TMZ combination therapy; 4-week recovery). For adjuvant PLX3397/TMZ PLX3397 treatment, dose escalation to the next highest cohort may occur after all patients have completed an 8-week DLT-observation period (i.e.,

2 cycles of adjuvant treatment). For patients participating in Phase 1b, intra and inter patient dose escalation to a higher dose level/schedule will be permitted after that dose level/schedule has been established to be safe.

Prior to dose escalation, safety data will be collated and reviewed by the Sponsor and study sites by teleconference. A dose level will be considered unacceptable if 2 or more patients of the 6 eligible patients experience a DLT (see below). Should all 7 patients in the Cohort be analyzable for adverse events, only the first 6 will be considered in the determination of DLTs. A patient who misses more than 7 days of PLX3397 administration during the 7-week dosing period of Cycle 1 (4 weeks) and Cycle 2 (3 weeks) for reasons other than having had a DLT will be replaced. If 2 or more patients in a Cohort experience a DLT, no patients in the Cohort will be replaced.

If 2 or more of the first 6 patients in Cohort -2 (600 mg/day of PLX3397; 5 days/week [M-F]) experience a protocol-defined DLT, the combination will be considered too toxic and the study will be discontinued.

### 13.13.2 Dose-Limiting Toxicities

Dose-limiting toxicities will be assessed using CTCAEv4 grading criteria. During the Phase 1b portion of the study, the DLT window will consist of 11 weeks (1 week PLX3397 run-in, 6 weeks of PLX3397 in combination with RT/temozolomide, and 4 weeks of post-RT recovery). The following will be considered DLTs:

#### Hematologic DLTs

- Grade  $\geq 3$  febrile neutropenia
- Grade 4 neutropenia lasting for  $>7$  days (growth factor support allowed)
- Grade 3 thrombocytopenia (platelets  $\leq 50.0/\mu\text{L}$ ) lasting for  $>7$  days

Grade 3-4 lymphopenia is NOT considered a DLT.

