#### Non-hematologic DLTs

- Any Grade  $\geq 3$  non-hematologic toxicity, **probably related to study drug**, EXCEPT for the following related AE's:
  - Grade  $\geq 3$  neurologic deficits considered to be due to the effects of tumor, resection, or expected post-surgical morbidities
  - Seizures of any grade, as this is commonly observed in this patient population
  - Grade  $\geq 3$  thromboembolic event, as this is commonly observed in this patient population
  - Grade 3 nausea, vomiting, or diarrhea that resolves to Grade  $\leq 2$  within 3 days of onset
  - Grade 3 headache, insomnia, or amnesia that resolves to Grade  $\leq 2$  within 14 days of onset
  - Grade 3 fatigue that resolves to  $\leq$ Grade 2 within 21 days of onset

- Grade 3 AST or ALT that resolves to  $\leq$ Grade 2 within 21 days of onset
- Grade  $\geq$ 3 CPK, GGT, ALP, hypomagnesemia, or hypophosphatemia that is felt by the investigator to be clinically insignificant
- Alopecia of any Grade.

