### 13.14 Dose Modification

#### 13.14.1 Phase 1

PLX3397 or temozolomide dose reductions and interruptions will be permitted during the 11-week DLT window (Cycle 1 through Cycle 2, i.e., 1 week PLX3397 run-in, 6 weeks of PLX3397 + RT + temozolomide, and 4 weeks of post-RT recovery) only if a patient experiences a DLT (see [Section 13.13.2](#) Dose-Limiting Toxicities). PLX3397 interruptions during the 11-week DLT window are also permitted for Grade 3 vomiting that persists despite optimal supportive care.

If a patient experiences a DLT during the 11-week DLT window, treatment continuation at a lower dose may be permitted at the discretion of the Investigator and in consultation with the Medical Monitor. PLX3397 dose reductions should occur in increments of 200 mg/day, depending on the toxicity grade, as noted in [Table 3](#), PLX3397 Dose Modifications. For dose reductions see [Section 13.13.1](#) Dose Escalation.

If dose interruption continues after the patient's scheduled C3D1 PLX3397 dose administration, the patient should discontinue study treatment and have the procedures outlined in [Section 13.11](#) End of Treatment.

During the adjuvant treatment period, PLX3397 or temozolomide dose reductions and interruptions will be permitted in consultation with the Medical Monitor. PLX3397 dose reductions should occur in increments of 200 mg/day, depending on the toxicity grade, as noted in [Table 3](#) PLX3397 Dose Modifications. For dose reductions see [Section 13.13.1](#) Dose Escalation.

If a patient experiences a DLT, temozolomide dose reduction should be made according to the prescribing information noted in [Attachment 4](#) and also summarized in [Section 16](#).

### 13.14.2 Phase 2

Phase 2 will not include a separate dose escalation design, as there has been no delayed toxicity observed for PLX3397 in extensive nonclinical and clinical evaluations to date, and temozolomide is given at a lower intensity schedule compared to the daily schedule during concomitant radiation therapy. During Phase 2, reduction/interruption of dosing for adverse events may take place at any time during the study according to the guidelines in Table 3.1, Table 3.2, and Table 3.3.

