**Table 3: PLX3397 Dose Modification Guidelines for Treatment-Related Toxicities, Excluding Liver Function**

All Drug-Related Toxicities	Frequency	When to Hold or Stop	When to Restart and Restart Dose (See Table 2 for dose levels.)
Grade 3 or 4 neutropenia	1st Appearance	Interrupt until ANC recovers to $\geq 1 \times 10^9/L$ ; growth factor support permitted	If recovered to ANC $\geq 1 \times 10^9/L$ in $\leq 7$ days, resume at same dose.
			If not recovered to ANC $\geq 1 \times 10^9/L$ after 7 days, reduce dose by 1 dose level.
	2nd Appearance	Interrupt until ANC recovers to $\geq 1 \times 10^9/L$ ; growth factor support permitted	If recovered to ANC $\geq 1 \times 10^9/L$ in $\leq 7$ days, reduce dose by 1 dose level.
			If not recovered to ANC $\geq 1 \times 10^9/L$ after 7 days, reduce dose by 2 dose levels.
3rd Appearance	Interrupt until ANC recovers to $\geq 1 \times 10^9/L$ ; growth factor support permitted	If recovered to ANC $\geq 1 \times 10^9/L$ in $\leq 7$ days, reduce dose by 1 dose level.	
		If not recovered to ANC $\geq 1 \times 10^9/L$ after 7 days, discontinue permanently.	
4th Appearance	Discontinue permanently; growth factor support permitted	N/A	
Grade 3 or 4 febrile neutropenia	1st Appearance	Interrupt until ANC and fever recover; provide growth factor support	If recovered to ANC $\geq 1 \times 10^9/L$ and $T \leq 38^\circ C$ in $\leq 7$ days, reduce dose by 1 dose level.
			If not recovered to ANC $\geq 1 \times 10^9/L$ after 7 days, discontinue permanently.
	2nd Appearance	Interrupt until ANC and fever recover; provide growth factor support	If recovered to ANC $\geq 1 \times 10^9/L$ and $T \leq 38^\circ C$ , reduce dose by an additional 1 dose level.
If not recovered to ANC $\geq 1 \times 10^9/L$ after 7 days, discontinue permanently.			
3rd Appearance	Discontinue permanently; provide growth factor support	N/A	
Grade 4 thrombocytopenia	1st Appearance	Interrupt until PLT $\geq 75 \times 10^9/L$	If recovered to PLT $\geq 75 \times 10^9/L$ $\leq 7$ days, resume at same dose.
			If not recovered to PLT $\geq 75 \times 10^9/L$ after 7 days, reduce dose by 1 dose level.
	2nd Appearance	Interrupt until PLT $\geq 75 \times 10^9/L$	If recovered to PLT $\geq 75 \times 10^9/L$ in $\leq 7$ days, reduce dose by 1 dose level.
			If not recovered to PLT $\geq 75 \times 10^9/L$ after 7 days, reduce dose by 2 dose levels.

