## **21.0 STATISTICAL ANALYSIS**

### **21.1 General Statistical Considerations**

#### **21.1.1 Phase 1b Portion**

The objective of the Phase 1b portion of this study is to determine the recommended Phase 2 dose (RP2D) of PLX3397 when combined with concurrent radiation therapy and temozolomide. Two expected dose levels are specified for testing, with one or more lower doses to be evaluated if the starting dose of 800 mg/day is above the MTD. For each dose level, 7 patients will be accrued to assure that there will be 6 patients eligible for evaluation of toxicity. A patient registered to the study who is found retrospectively not to meet the study eligibility criteria, who does not receive any PLX3397, or who is considered non-evaluable during the toxicity evaluation period for reasons not related to study drug will be excluded from evaluation of DLT and replaced.

Patient accrual will be suspended after each dose cohort is enrolled until there is sufficient information collected to make a decision relative to dose escalation. A dose level for PLX3397 will be considered acceptable if no more than 2 patients of the 6 eligible patients experience a DLT. Should all 7 patients be analyzable for adverse events, only the first 6 will be considered in the determination of DLTs. If the current level is considered acceptable, then dose escalation will occur and the protocol will be reopened. Otherwise, the preceding acceptable dose level will be declared the MTD. The Sponsor, together with the study investigators, will evaluate the safety of each cohort prior to dose escalation.

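### The only platelet DLT is wrong as written: the Grade 3 label leaves out sustained Grade 4 thrombocytopenia, and its bracket (≤50.0/µL) drops a factor of 1,000

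*Combined protocol and SAP*

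**What the plan says.** Section 13.13.2, under Hematologic DLTs, has three qualifying items: febrile neutropenia of Grade ≥3, Grade 4 neutropenia beyond 7 days, and "Grade 3 thrombocytopenia (platelets" followed by ≤50.0/µL in the bracket, beyond 7 days. The Synopsis repeats the platelet item with the same label and the same number. An exclusion follows the list: "Grade 3-4 lymphopenia is NOT considered a DLT". The next list opens with a Grade ≥3 catch-all, but it is confined to "non-hematologic toxicity". Section 13.13.2 says DLTs are graded by CTCAE v4.

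The DLT count drives three things:

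- **Cohort decision, Section 13.13.1:** "A dose level will be considered unacceptable if 2 or more patients of the 6 eligible patients experience a DLT". Section 21.1.1 sets a different cut-off: "A dose level for PLX3397 will be considered acceptable if no more than 2 patients of the 6 eligible patients experience a DLT".
- **Study stop, Section 13.13.1:** if 2 or more of the first 6 patients in Cohort -2 "experience a protocol-defined DLT, the combination will be considered too toxic and the study will be discontinued".
- **Dose modification, Section 13.14.1:** in the 11-week window, reductions and interruptions are allowed "only if a patient experiences a DLT". The one exception is an interruption for persistent Grade 3 vomiting.

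Other platelet thresholds in the protocol body are in units of 10^9/L: at least 100 for eligibility, 75 for restarting PLX3397 in Table 3, and below 50 for reducing temozolomide in Table 8. The only platelet row in Table 3 is "Grade 4 thrombocytopenia".

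**The concern.** There are two defects in one line.

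The first is the label. The same short list separates Grade ≥3, Grade 4 and Grade 3-4, so a bare Grade 3 reads as Grade 3 alone. On that reading a platelet count in the Grade 3 range for more than 7 days is dose-limiting, while a worse count for the same time is not. No other line picks it up.

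The second is the bracket, which is printed in a unit that makes the threshold 1,000 times too low. It therefore cannot be used as it stands to settle what the label means.

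At stake is a count in six patients that decides escalation and can stop the study. The Cohort -2 stop is tied to DLTs as the protocol defines them, so the definition should not depend on readers repairing it. There is also a treatment consequence. Read literally, sustained Grade 4 thrombocytopenia never opens the route to a hold or reduction under Section 13.14.1.

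**Working it through.** **Inputs**

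- Printed bracket: ≤50.0/µL (Synopsis and Section 13.13.2).
- Temozolomide reduction: platelets <50 × 10^9/L (Table 8).
- Equivalence: Attachment 4, section 2.1, equates 50 × 10^9/L with 50,000/µL.
- Grade 4 platelets: below 20,000/µL (Attachment 4, section 6.1). The documents do not reproduce the CTCAE v4 cut-offs, so this figure comes from the temozolomide label.

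**Step 1, the unit.** 1 L = 10^6 µL, so 50 × 10^9/L = 50 × 10^9 / 10^6 = 50,000/µL. The printed 50.0/µL is 50 × 10^6 / 10^9 = 0.05 × 10^9/L. The ratio is 50,000 / 50 = 1,000. The number is identical in both places where it appears.

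**Step 2, label against bracket.** Let c be the Grade 4 cut-off, so that Grade 4 means a count below c.

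- Printed unit: every count ≤50/µL is below c as long as c exceeds 50/µL. All such counts are Grade 4, so no patient is both Grade 3 and inside the bracket.
- Corrected unit: the bracket is ≤50,000/µL with no lower bound. It includes every count below c as long as c is under 50,000/µL. It therefore takes in Grade 4, which the label leaves out.

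The conflict holds for any c between 50 and 50,000/µL. The label's 20,000/µL lies in that range, and the conclusion does not depend on that exact value.

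**Step 3, coverage.** The other two hematologic items are neutropenic, and the Grade ≥3 catch-all is non-hematologic. Grade 4 thrombocytopenia has no other route into the DLT count.

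**Step 4, effect on the count.** The rules count patients, not events. Among the six, let k be the patients who have a DLT as literally defined, and a the patients whose only qualifying event is Grade 4 thrombocytopenia beyond 7 days. A patient who also spends more than 7 days at Grade 3, or has another listed DLT, is already in k. The literal count is k and the intended count is k + a.

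- Section 13.13.1 (unacceptable at 2 or more): the decision changes when k < 2 ≤ k + a. That is k = 1 with a ≥ 1, or k = 0 with a ≥ 2.
- Section 21.1.1 (acceptable up to 2, so unacceptable at 3 or more): it changes when k < 3 ≤ k + a. That is k = 2 with a ≥ 1, k = 1 with a ≥ 2, or k = 0 with a ≥ 3.

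With a single affected patient, the decision changes at exactly one other DLT patient under Section 13.13.1, and at exactly two others under Section 21.1.1. The disagreement between those two sections is a separate matter.

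**Step 5, frequency.** The documents give no rate for Grade 4 thrombocytopenia lasting more than 7 days in this window. The closest context is Table 7 of Attachment 4: Grade ≥3 thrombocytopenia in 8/288 = 2.8% (printed as 3%) of patients on concomitant radiotherapy plus temozolomide. That figure is without PLX3397, includes Grade 3, and has no duration condition.

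**The case against.** The strongest reply is that the meaning can be recovered. Nobody would apply a threshold of 50 platelets per microlitre when eligibility, restart and temozolomide reduction sit at 100, 75 and 50 × 10^9/L. With the multiplier restored, a bracket without a floor already captures Grade 4. The sponsor and sites review safety data before each escalation, and a review that counted Grade 3 as dose-limiting but passed over Grade 4 is hard to picture. Table 3, to which Section 13.14.1 points for reductions after a DLT, has a Grade 4 platelet row. That also suggests Grade 4 was meant to count, although the evidence is weak: the table is set out under Phase 2 and has no Grade 3 platelet row.

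Most of this stands, and it limits the weight of the point. CTCAE v4 grading makes the unit slip alone nearly harmless, and investigators would probably count Grade 4. What it does not do is correct the text. The list distinguishes grades elsewhere, and label and bracket still contradict each other after the unit is repaired.

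On treatment, a reader might infer that a patient with sustained Grade 4 platelets must stay on drug. The documents do not support that. Section 13.15 lets study drug be discontinued for an adverse event or at the investigator's discretion, and Section 26.0 allows immediate departures to remove an apparent hazard. What is lost on the literal reading is the hold or reduction, and only after day 7, because the corrected wording also requires more than 7 days.

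**Conclusion.** The criterion is wrong as written, with minor to moderate severity. The bracket is low by a factor of exactly 1,000. The label literally omits sustained Grade 4 thrombocytopenia, and no unit reconciles the two. The consequence is confined to patients with no other qualifying DLT. Each such patient lowers the count by one, and the cohort decision changes only when adding them carries the count from below the cut-off to or above it.

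Three stronger readings are tempting and not supported:

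- That the unit error leaves platelet toxicity uncounted in practice. CTCAE v4 grading and the protocol's other platelet thresholds argue against this.
- That every patient with Grade 4 platelets is missed. Some would already count through another DLT or through more than 7 days at Grade 3.
- That a rate of wrong decisions can be given. Section 6.1 of Attachment 4 reports Grade 4 thrombocytopenia in 48/879 (5.5%) of patients aged 70 or under in the first cycle. That is the label's whole safety database with no duration condition, and is less apt than the 3% above. Neither figure is a rate for this event with PLX3397.

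The conclusion assumes only that the Grade 4 cut-off lies between 50 and 50,000/µL. No sample size, power or significance figure depends on it.

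**What to change.** In both the Synopsis and Section 13.13.2, replace the platelet item with: *Grade ≥3 thrombocytopenia (platelets <50 × 10^9/L) lasting >7 days*. This uses the unit and cut-off already in Table 8. It changes ≤ to <, so a count of exactly 50 × 10^9/L no longer meets the bracket; the amendment should say so.

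The cost is protocol wording in two places, with no change to sample size, visits or procedures. If any Phase 1b cohort has already been judged, check once that sustained Grade 4 platelet events were counted as DLTs, because the recommended Phase 2 dose rests on those counts.
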